7. RECRUITMENT METHODS

Caregiver subjects will be recruited via the IRB approved HARP Population Study (RSRB00068059), a research registry run by the current study's Investigators. In compliance with procedures of the Population Study protocol, subjects of the Population Study consent to allow HARP Population Study researchers to share subjects' identifiable data (both name and contact information) with investigators conducting HARP research at the University of Rochester; in addition, they consent to allow their data collected as part of the Population Study to be included in their research record for subsequent HARP studies they participate in, including the current study. All eligible participants will be provided with a study brochure, at their in-person screening visit and given information about the study.

8. CONSENT PROCESS

Caregiver Consent: Eligible subjects who have agreed to have their contact information shared will be contacted by the project coordinator and then scheduled for their semi-structured interview. We are requesting a waiver of documentation of consent for the caregivers because the research is no greater than minimal risk and the semistructured interview questions will be addressing a topic where written consent is not normally required. The waiver won't affect the rights and welfare of the subjects. Eligible subjects will have an opportunity to review the information letter with the interviewer and ask questions and have their questions answered to their satisfaction prior to the start of their semi-structured interview. The process of reviewing the information letter will be conducted in a manner to facilitate questions from potential study subjects. If a study team member is unable to answer a question, an investigator will be contacted. All questions from potential subjects should be answered prior to the interviewer initiating the semi-structured interview. All subjects will receive a copy of the study information letter. No subjects will be involved in research activities unless an investigator or a designated study staff member has completed a thorough review of the information letter with the subject.

The information that is given to the subject shall be in language understandable to the subject. Potential study subjects will be given ample time to read and consider the information letter. All subjects will be reminded of the voluntary nature of study participation. Research personnel will explain the study, the voluntary nature of participation, the study's potential benefits and risks, and alternatives. An explanation of risks will include information that questions asked may cause subjects to feel uncomfortable or upset. They will be informed that they may withdraw from the study at any time for any reason without negative consequences and receive full reimbursement for the study. Consent will be obtained during Aim SA3 in the same manner as was done under previously approved Aims SA1 and SA2. We are requesting a waiver of documentation of consent for caregivers who enroll in SA3 because the research is no greater than minimal risk and the interview questions will be addressing a topic where written consent is not normally required. The waiver won't affect the rights and welfare of the subjects.

9. STUDY PROCEDURES

Caregiver Subjects: The card sort intervention will be conducted by a trained research assistant (RA). The intervention will be conducted via ZOOM, audio-recorded, and typically last between 45-60 minutes. Interview questions will focus on (1) how participants characterize social connectedness and activities they use to connect, (2) social connections that are important/meaningful to them, (3) what makes social connections easier and more difficult (including barriers), (4) how their social connections may have changed with the caregiver role, (5) how or whether they prioritize social connectedness in their day to day lives, and (6) the advice they would give to new caregivers about maintaining or improving social connections. We will use a laddered technique with early questions designed to be minimally intrusive and deliberately broad to allow participants to focus on the experiences of social connection important to them. Later questions will be built off the earlier questions and probe for detail and specific examples of participants' unique experiences with social connectedness. The semi-structured interviews will be audio recorded so that the full conversation can be transcribed for later analysis, and subjects will be informed of this before discussion begins. No identifying information (for example, subject names, or other details shared during the discussion) will be included in the transcript. The audio recording will be transferred from the recording device to a secure computer in the School of Nursing, after which the recording will be deleted from the recording device. The de-identified electronic version of the transcript will remain on the School of Nursing's secure computer where it will be accessible only to the study PI and project team members. For Aim SA3, new measures will be used and are based on the work completed in AIMS SA1 and SA2.

Caregiver subjects participating in SA3: Questions included in the last few slides of the Power Point presentation of the card sort tool will be read to the participants, and individual semi structured interviews will also be conducted. The questions in the Power Point presentation of the card sort tool and the semi-structured interviews will be conducted by a research assistant (RA) trained in qualitative interviewing techniques. A second research assistant may also join the call for training purposes. Because the interviews will be recorded using Zoom video and audio, subjects will need to have a stable internet connection to participate.

10. AUDIO/VIDEO RECORDINGS

We will use audio recorders and Zoom which are HIPPA-compliant and URMC-approved. The audio files will be uploaded onto a secure database within the School of Nursing usually within 24 hours (occasionally interviews occurring off site on a Friday afternoon will be uploaded on Monday morning). The audio recordings will be transcribed and the transcripts deidentified. Audio recordings will then be used to verify the transcription accuracy. Audio recordings will be archived with a unique identifier for linkage to the other data and will be kept for 3 years. It is occasionally helpful during data analysis to listen to the original audio recording to verify the intent of the speaker

(e.g., para linguistic cues of humor, sarcasm, or emotion that are not contained in the transcription). The archived recordings will be housed on a University of Rochester School of Nursing firewalled, password-protected, and HIPAA compliant server and in BOX which is URMC-approved. Unique identifiers will be used to maintain future linkage between the archived conversations and the Analytic File.

11. RISKS TO SUBJECTS

Potential risks to subjects: minimal risk for all procedures.

For research assessments—self-report questionnaires and semi-structured interviews—the primary risk is invasion of privacy, breach of confidentiality (if safety issues are detected), or mild reactions of distress or fatigue. All assessment measures and procedures have been safely used previous research with older adults; no sustained negative effects from assessments are expected, but negative outcomes cannot be ruled out. For Aim SA3, we will minimize potential risks to subjects by having the trained interventionists report to the PI any concerns that may arise during administration of any of the measures.

Private identifiable information collection: Study coordinators and research team members will have access to individually identifiable private information about human subjects.

For the intervention, Connect for Caregivers, the primary risk of is emotional distress or fatigue. Subjects may think about stressors, negative life events, and caregiving burden/distress; they will receive support from the interventionist for such experiences. No sustained negative effects are expected, but negative outcomes from behavioral interventions cannot be ruled out. The study PI ([name]) will provide weekly (and as needed) supervision. In addition, [name] (Co-I) is a clinical geropsychologist and is experienced in working with older adults, including those experiencing emotional distress and will available as needed.

Regarding alternative interventions, subjects will not be prohibited from seeking out supportive social services, or mental health services (for ethical reasons).

12. POTENTIAL BENEFITS TO SUBJECTS

Caregiver subjects *might* find identifying their own barriers and facilitators to social connection helpful. They may further benefit from feelings of altruism connected with participation in research designed to better understand the mental health needs and experiences of community-residing older adults. There are no other anticipated benefits.

13. COSTS FOR PARTICIPATION

None anticipated. The location of the caregiver interviews will be by ZOOM due to COVID-19 safety guidelines. The location for the care manager focus group will be via ZOOM.

14. PAYMENT FOR PARTICIPATION

Each subject will be paid \$20 by check for their participation in each of the three parts of SA3, for a maximum total of \$60 per subject..

15. SUBJECT WITHDRAWALS

We do not anticipate any circumstances under which participants will be withdrawn by the investigator. Subjects are free to withdraw at any time without negative consequences. Subjects may also refuse to answer any individual questions.

If a subject voluntarily withdraws from the study we will note the reason. We will use the data already collected unless the subject indicates they want the data destroyed. In the event of the latter, subjects who withdraw from the study will be replaced.

16. PRIVACY AND CONFIDENTIALITY OF SUBJECTS AND RESEARCH DATA

In order to protect the confidentiality of subject information, we will take a number of precautions. These include training research interviewers in confidentiality procedures; entry and storage of data using coded identification labels; maintenance of project computers in secure locations with restricted access by enforced password protection; use of HIPAA compliant data management software (REDCAP). Back-ups of all study files will be made daily to allow for recovery of data due to disk failure. All data, including assessment measures, will be obtained with the written consent of the subject. Information pertaining to individual subjects will be released with the subject's informed and written consent only, except in unusual cases where withholding the information might pose a serious risk or danger to the subject or others. All data will be identified by a uniquely coded study number assigned to each subject. Access to the master list of study numbers will be restricted to [name] and the CRC. Confidentiality will be further maintained by the storage of "hard copy" data in locked files in a locked office. Access to computerized data is restricted and subject to review by [name]. Publications or presentations will report only cumulative data or descriptions certain to maintain participants' anonymity. All data collection involving human subjects will be HIPAA compliant. Audio recording devices will be kept on the person of the study interviewer who will return immediately to the School of Nursing with audio recorder after the interview has been completed. The audio recording will be immediately uploaded to the School of Nursing secure server, and once the upload is complete, the recording will immediately be deleted from the recording device. Since two recording devices are used to insure protection from any unexpected technical problems, both recording devices will have the recordings deleted as soon as uploads are complete after each interview. All data involving human subjects will be stripped of any identifiers; the data will be stored in a secure HIPAA compliant program called REDCAP, which manages protected health information in a HIPAA compliant manner. Audio recordings of semi-structured interviews will be transcribed and then kept for three years

Risks associated with emotional distress or fatigue will be minimized by employment of research personnel with appropriate backgrounds and experience and work with psychological factors and elderly subjects. The baseline research interview will last

approximately two hours in total. Given the length of time involved for this assessment, and concerns regarding subject health and well-being, subjects will be reminded that if they become fatigued, they may terminate the interview at any time, and that the interview can be conducted over multiple sessions as needed. Research personnel will further be trained to recognize potential signs of fatigue among elderly subjects, and to actively suggest alternative data collection strategies (including telephone-based and mail-in interviews), in order to reduce the possibility of overwhelming study subjects and to ensure completeness of data collection. These strategies have been employed effectively in the PI and Co-I's past research involving older adult populations. During the course of the semi-structured interviews, the researcher will monitor subjects' reactions for signs of distress or fatigue. If necessary, subjects may take breaks from the interview, or complete the interview over several sessions if fatigue becomes a concern.

17. DATA / SAMPLE STORAGE FOR FUTURE USE Not applicable

18. DATA AND SAFETY MONITORING PLAN Attached

19. STATISTICAL ANALYSIS PLAN

Testing the 'Connect for Caregivers' discussion prioritization tool: Aim 3 involves a pilot test of the Connect for Caregivers discussion prioritization tool with a sample of caregivers who report disconnectedness (n=5). Caregivers will receive the psychoeducation materials on connectedness (delivered by research staff), complete the card sort task to identify personal barriers to connectedness, and received personalized community resources to address their identified barriers to connectedness. Using the methodology described in Aim 1 for semi-structured interviews, caregivers will provide feedback on the experience of the intervention, including ease of completing it and potential utility. Participants will also complete quantitative measures of their motivation to increase social connectedness via self-report measures that were developed to test mechanisms posited by Self-Determination Theory that we have used with success in prior studies with social connectedness interventions (i.e., Perceived Competence Scale and Perceived Autonomy Scale). Participants will complete these measures at their initial screening interview (as described in the STAR Core Battery above) and again after completing the Connect for Caregiver intervention. We will use descriptive statistics to compare changes in mean scores pre and post completion of the tool.

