4. STUDY DESIGN

This is a mixed method intervention development study using semi structured interviews (SA 1a and 2) and a focus group (SA 1b) to develop and refine a psycho-behavioral intervention that we will then pilot test (SA 3) using a non-randomized single arm prepost approach.

Study outcomes/endpoints

Aim 3: To investigate whether Connect for Caregivers—a card sort discussion prioritization tool combined with personalized education and resources—is associated with a signal for efficacy for changing connectedness. We will be conducting AIM SA3 in this phase of the study, as approved in the original study Protocol.

- Outcome 3a: A **non-random sample of caregivers (n=5)** will complete the Connect for Caregivers tool with a research assessor, including discussing psychoeducational materials on the benefits of social connectedness, completing the card sort to identify personal barriers to connectedness, and reviewing personalized community resources to address those barriers. Using semi-structured interviews, they will provide feedback on the experience of the intervention, including ease of completing it and potential utility as well as the extent to which they experienced the SDT mechanisms of: autonomy, competence, and relatedness while completing the tool and after completing it.
- Outcome 3b: Participants will also complete quantitative measures of their motivation to increase social connectedness via self-report measures that assess mechanisms posited by Self-Determination Theory (i.e., autonomy, competence, relatedness). Participants will complete these measures at their initial screening interview and again after completing the Connect for Caregiver intervention.

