6. INCLUSION AND EXCLUSION CRITERIA

Caregiver Inclusion criteria (assessed at the HARP Population Study RSRB00068059, screening assessment):

- 1) Caregiver (age 50 or older) for a community-dwelling family member with ADRD, living with (or in close proximity to) family member with dementia.
- 2) Elevated caregiving distress: Above population mean (>11) on 10-item Perceived Stress Scale (PSS-10) and/or at least moderate caregiver strain (score >= 5) on the Modified Caregiver Strain Index (MCSI).
- 3) Social connectedness: UCLA Loneliness Scale: Short Form score of equal to or greater than 6 (n=10; Short Form score of 3-5, n=10).
- 4) Able to provide informed consent to participate in the research study.
- 5) For phase SA2, a stable internet connection for using Zoom video and audio.

Caregiver Exclusion criteria (assessed at the HARP screening assessment):

- 1) Non English speakers because our primary community partner agency (Lifespan) cannot currently accommodate non-English speaking clients.
- 2) Current problem drinking on the AUDIT-C (score of 5 or greater indicating exclusion).
- 3) Current non-alcohol psychoactive substance abuse (MINI Neuropsychiatric Interview), psychotic disorders (current and lifetime, MINI), bipolar disorder (MINI), and current mood disorder with psychotic features (MINI).
- 4) Significant cognitive impairment (MOCA <22) and those with hearing problems that preclude completion of interviews will be excluded.

Vulnerable Subjects: Individuals who are 50 years of age and older with social risk factors for poor mental and physical health outcomes will be included. The results of this study will inform future research and clinical interventions aimed at improving mental health treatment for older caregivers.

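### The pre score for the two motivation scales is set at screening, with no limit on the time from there to the session or from the session to the post score

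*Combined protocol and SAP*

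**What the plan says.** Two sections fix the timing of the scales, and they agree. Section 4, Outcome 3b: "Participants will complete these measures at their initial screening interview and again after completing the Connect for Caregiver intervention". Section 19 repeats this with a cross-reference: "Participants will complete these measures at their initial screening interview (as described in the STAR Core Battery above) and again after completing" the intervention. The analysis in Section 19 is one sentence: "We will use descriptive statistics to compare changes in mean scores pre and post completion of the tool".

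The rest of the timeline comes from other sections:

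- **Screening.** Section 6 heads the eligibility criteria "assessed at the HARP Population Study RSRB00068059, screening assessment". Section 7 says that brochures are given to eligible participants "at their in-person screening visit", and that registry data may enter the record of later HARP studies. It sets no limit on the age of those data.
- **From screening to session.** Section 8 says that eligible caregivers who agreed to share their contact details "will be contacted by the project coordinator and then scheduled for their semi-structured interview". It gives no maximum time.
- **Session.** Section 9 describes a single Zoom session of 45 to 60 minutes.
- **Other services.** Section 11: "subjects will not be prohibited from seeking out supportive social services, or mental health services".
- **SA3 contacts.** Section 14 pays for three parts of SA3 and does not say what they are.

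**The concern.** Section 19 labels the result as change across completion of the tool. That label fits if the pre score is taken shortly before the tool is used. It fits less well if the pre score comes from a registry visit at an unstated earlier date, because the difference then also holds whatever changed between that visit and the session.

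This change is the quantitative part of the Aim 3 signal for efficacy, beside the interview feedback of Outcome 3a. With no control arm, nothing in the analysis removes change from before the session. The interval may also differ between the five caregivers, and the plan does not say that it will be reported. A reader of the results could not tell whether a mean change spans days or many months.

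**Working it through.** The plan states no figure for this point, so there is none to reproduce. It gives no interval, standard deviation, retest data or service-use data. The check is a comparison of sections, followed by the little arithmetic that n = 5 allows.

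**1. Which occasion supplies the pre score?**

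| Reading | Source | Stated time to session |
|---|---|---|
| HARP registry screening (default reading) | Sections 4 and 19 name screening; Sections 6 and 7 describe only this one | None |
| One of the three paid parts of SA3 | Section 14; parts not defined | None |
| A baseline interview of about two hours | Section 16; not linked to SA3 or to these scales | None |

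The first reading follows most directly from the text. The other two are possible, but no section ties them to the two scales. On none of them is there a window.

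**2. Which intervals make up the reported change?** There are two: pre score to session, and session to post score. Sections 4 and 19 say only that the post score comes after the intervention. Neither interval has a stated limit.

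**3. What does the reported change contain?** For one caregiver, write S for the score at screening, B for the score just before the session and P for the post score. Then

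P − S = (B − S) + (P − B).

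The label in Section 19 describes P − B. If the pre score is the screening score, the plan reports P − S. The plan does not provide for B, so the part B − S cannot be seen or separated.

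**4. How does B − S enter the mean?** Assume that all five caregivers have both scores. If k of them have B − S = D points and the others have zero, the mean change moves by k × D / 5:

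- k = 1: 0.2 D
- k = 2: 0.4 D
- k = 3: 0.6 D
- k = 4: 0.8 D
- k = 5: D

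D is not given in the documents and may be zero. This shows only that one caregiver's shift carries a fifth of its size into the mean.

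**5. Does service use belong in B − S or in P − B?** Services used before the session fall in B − S and are unrelated to the tool. After the session the position differs. The session itself supplies personalized community resources (Sections 4 and 19), so taking them up may be part of the intended effect. For the second interval the problem is the missing window: a score on the day of the session and one after the resources have been used answer different questions.

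**The case against.** The strongest reply is that the gap changes little. The study has one arm and five participants, the analysis is descriptive, and the change could not be attributed to the session at any interval. It would stay uncontrolled after the fix. Moving the baseline is also a trade: motivation items repeated around a session of 45 to 60 minutes may invite recall and demand effects that a separate, earlier baseline avoids. All of this stands, and it keeps the point minor. It does not answer the mismatch between the label in Section 19 and the stated time of the pre score, and it gives no reason to leave the intervals unreported.

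A reader might also infer more than the documents support:

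- *That the gap is long.* No section says so. If one of the three parts of SA3 is a pre-session assessment, the gap could be short.
- *That the baseline occasion cannot be identified.* Sections 4 and 19 agree in naming the screening interview, and Sections 6 and 7 describe one. The limit on time is what is missing.
- *That Section 9 contradicts this baseline.* It says "For Aim SA3, new measures will be used and are based on the work completed in AIMS SA1 and SA2", but does not name those measures. Section 19 describes the two motivation scales as used in prior studies, so the new measures are probably something else.
- *That the undefined STAR Core Battery is a planning fault.* Its description may lie in text not supplied for review. The point does not rest on it.
- *That service use after the session contaminates the result.* It may be part of the effect, as noted above.

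**Conclusion.** The concern holds as a minor design point. As written, the pre score is tied to a screening interview. The only screening described belongs to another study, and neither the time to the session nor the time to the post score is limited. The change called pre to post completion of the tool can therefore include an undated pre-session period in which outside services are allowed.

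No size is claimed. The effect on the mean is k × D / 5, with D unknown and possibly zero. No test or error rate is affected. The conclusion rests on reading the screening interview of Sections 4 and 19 as the HARP assessment. If an SA3 part already gives the scales before the session, what remains is to name that part and state the windows.

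**What to change.** In Sections 4 and 19:

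- Give the two scales at an SA3 contact before the psychoeducation starts, and use that as the pre score. If one of the three parts of SA3 already does this, name it as the baseline instead.
- Keep the screening score as a descriptive second baseline, so that drift from screening to session can be seen.
- State a window for the post score.
- Report each participant's days from screening to session and from session to post score.

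The cost is a wording change and a few minutes per participant. Whether the post score needs a further contact depends on what the three parts of SA3 are. The downside is possible recall or demand effects from giving the scales close together; the retained screening score gives some view of this. The change remains uncontrolled and descriptive.

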1. PURPOSE OF STUDY

Connect for Caregivers is a mixed method intervention development pilot study. The purpose of the study is to develop and pilot test a single session behavioral intervention to help caregivers gain understanding of the importance of increasing social connectedness, awareness of their personal barriers to connectedness, and knowledge of local resources for promoting connectedness. The specific aims of this mixed method study are:

Aim 1 To characterize caregivers' understanding of their experiences of social connectedness and of their perceptions of barriers to social connectedness, including which barriers are most common, most problematic, and most difficult to change.

Aim 2 To use information provided by caregivers (in Aim 1) to develop a card sort discussion prioritization tool (*Connect for Caregivers*) that will systematize and routinize a process whereby caregivers and interventionists can collaboratively identify and prioritize personalized intervention targets for promoting connectedness.

Aim 3 To investigate whether *Connect for Caregivers* (a card sort discussion prioritization tool combined with personalized education and resources) is associated with a signal for efficacy for changing connectedness.

This submission is for conducting Aim SA3, the final phase of the study, as approved in the original study Protocol.

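### Aim 3 seeks an undefined efficacy signal for connectedness, but the planned quantitative analysis names only two motivation scales, in five caregivers with no control group

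*Combined protocol and SAP*

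**What the plan says.** Section 1 (Purpose of Study) and section 4 (Study Design) both state Aim 3 as finding out whether the tool "is associated with a signal for efficacy for changing connectedness". Neither section, nor section 19, says what result would count as a signal. Section 4 describes the pilot as "using a non-randomized single arm prepost approach", and section 5 fixes enrolment at 5.

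The quantitative outcome is 3b in section 4. There and in section 19 (Statistical Analysis Plan), participants complete "quantitative measures of their motivation to increase social connectedness". Outcome 3b lists three mechanisms: autonomy, competence and relatedness. Section 19 names two scales, "Perceived Competence Scale and Perceived Autonomy Scale", and none for relatedness. They are given at the screening interview and again after the intervention. The analysis is then a single sentence: "We will use descriptive statistics to compare changes in mean scores pre and post completion of the tool".

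Three other places bear on the point:

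- Section 6 uses the UCLA Loneliness Scale Short Form under the label of social connectedness, as an eligibility criterion at screening. No repeat is stated.
- Section 9 says that this phase will use new measures, without naming them.
- Section 19 refers back to a STAR Core Battery that the available text does not describe.

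Outcome 3a adds semi-structured interviews on the experience of the tool, its ease and usefulness, and the same three mechanisms.

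**The concern.** The aim and the analysis concern different things. The aim is about changing connectedness; the scales to be analysed are about motivation to become more connected. Even a large, precisely estimated rise in perceived competence or autonomy would leave the aim as worded unanswered.

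Two features of the design widen the gap. Without a control group, a change between screening and follow-up could reflect the passage of time, repeated testing or the way participants were selected, as well as the tool. With five people, a mean change carries wide uncertainty, and the plan does not commit to showing it.

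What is at stake is the conclusion. With *signal* undefined, a favourable shift in a mean could be written up as an efficacy signal for connectedness and carried into the case for a later trial, when the data could not bear that reading.

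**Working it through.** **1. Aim against measures.**

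| Element | Where | Content |
|---|---|---|
| Aim | Sections 1 and 4 | Efficacy signal for changing connectedness |
| Quantitative outcome | Section 4, Outcome 3b | Motivation, through autonomy, competence and relatedness |
| Scales named for analysis | Section 19 | Perceived competence, perceived autonomy |
| Connectedness-type scale named | Section 6 | UCLA Loneliness Short Form, screening only |
| Unspecified measures | Sections 9 and 19 | New measures; STAR Core Battery |

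No row gives a connectedness measure that is both taken after the intervention and analysed. The last row means that such a measure may exist, but none is named in the analysis.

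**2. Inputs for precision.** The sample size is 5 (sections 4, 5 and 19). Section 15 replaces a withdrawn participant only when that person asks for the data to be destroyed, so 4 complete pairs is a realistic case. The plan gives no SD, pre-post correlation, confidence level or precision target. There is therefore no figure of its own to reproduce, and 5 is best read as a feasibility number. The 95% level is my assumption.

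**3. Half-width of a 95% t-interval for a mean paired change.** In units of the SD of the within-person change, the half-width is t(0.975, n − 1)/√n.

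- n = 5: 2.776/√5 = 2.776/2.236 = 1.24
- n = 4: 3.182/√4 = 3.182/2 = 1.59

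With all five pairs, the observed mean change would have to exceed 1.24 times its own observed SD before the interval excluded zero.

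**4. Why pre and post means do not show this.** With complete data, the difference between the two means equals the mean paired change, so the point estimate is unaffected. Its precision depends on the SD of the change:

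SD(change) = √(s₁² + s₂² − 2·r·s₁·s₂),

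where s₁ and s₂ are the pre and post SDs and r is the correlation between each person's two scores. With equal SDs, s₁ = s₂ = s, this becomes s·√(2(1 − r)). In single-score SDs the half-width with 5 pairs is then 1.242·√(2(1 − r)):

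| Assumed r | √(2(1 − r)) | Half-width |
|---|---|---|
| 0 | 1.414 | 1.76 |
| 0.5 | 1.000 | 1.24 |
| 0.8 | 0.632 | 0.79 |

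The same two means and SDs are thus compatible with half-widths that differ more than twofold (1.76/0.79 = 2.2). Only the paired changes settle which applies.

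**5. Attribution.** Step 3 concerns sampling error alone. An interval that excluded zero would show that scores had moved. In a single arm it would not show that the tool moved them.

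**The case against.** The best defence is that this is a five-person development pilot. Descriptive analysis is the right choice, a hypothesis test would tell almost nothing, and the interviews carry much of the evidence. Descriptive statistics on changes in the same people can ordinarily include the paired change and its SD. All of this stands. A reader might infer that the plan rules out paired reporting, or that it is wrong to be descriptive. The text supports neither: precision is left unspecified, not excluded, so that part of the point is close to a missing detail.

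A reader might also infer that any rise in a mean will be declared a signal. No section states such a rule. The supportable criticism is that *signal* has no definition.

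Finally, a reader might infer that connectedness is not measured at all after the session. The unnamed new measures, the undescribed battery and the listing of relatedness prevent so firm a statement. Relatedness is close to connectedness, but Outcome 3b treats it as a mechanism of motivation and section 19 gives it no scale.

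The defence does not remove the mismatch. The interviews do not turn competence and autonomy scores into measures of connectedness, and they supply no comparison group.

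**Conclusion.** The point holds as a minor one. As written, the planned quantitative comparison cannot support the conclusion that Aim 3 attaches to it, for three reasons: the named scales address motivation, there is no control group, and *signal* is undefined. The uncertainty is large, at ±1.24 SDs of the change with 5 pairs and ±1.59 with 4.

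The half-widths assume a 95% level and approximately normal changes. The conversion to single-score SDs also assumes equal SDs and the stated range of correlations, none of which comes from the documents. The mismatch and the lack of a control group depend on none of these assumptions. The statement about what is measured is limited to the measures that the documents name.

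**What to change.** In section 19, replace the last sentence with wording such as:

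> For each scale we will report the mean within-person change (post minus pre) with its SD and 95% t-interval, and the number of complete pairs. These results describe the size and variability of change in motivation. No conclusion about efficacy, or about change in connectedness, will be drawn from them, whatever the direction of the change or the position of the interval, because there is no control group and these scales do not measure connectedness.

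If a relatedness scale is used, name it there and summarise it in the same way, so that sections 4 and 19 agree.

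Then align Aim 3 in sections 1 and 4, for example: *to estimate the size and variability of pre-post change in motivation to increase connectedness*. The phase is described as conducted "as approved in the original study Protocol". If the approved wording must stay, add one sentence to section 4 saying that the quantitative data are for estimation only.

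If the sponsor prefers to keep connectedness in the aim, an option is to repeat the UCLA Loneliness Short Form after the session and report its change descriptively. Section 19 describes the five as caregivers reporting disconnectedness. Selection on a high screening score can by itself produce an apparent improvement, and the report should say so. The bar on efficacy conclusions would remain.

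**Cost.** The main fix needs no new data and very little analysis time, but possibly a minor amendment. The stated claim becomes less favourable, and the interval will be wide, with a normality assumption that 5 pairs cannot check. The optional repeat adds one short questionnaire.
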